6.2.1 Primary Adverse Event

A Primary AE is one of the following events occurring within seven (7) days following an AF ablation procedure with the study catheter:

Table 6-1 Primary Adverse Events

PRIMARY ADVERSE EVENT	DESCRIPTION / CRITERIA
Death	Patient death directly related to the device or procedure and occurs at any time during or after the procedure.
Atrio-Esophageal Fistula*	Is defined as a connection between the atrium and the lumen of the esophagus. Evidence supporting this diagnosis includes documentation of esophagus erosion combined with evidence of a fistulous connection to the atrium such as air emboli, an embolic event, or direct observation at the time of surgical repair. A CT or MRI scan is the most common method of documentation of an atrio-esophageal fistula.
Cardiac Tamponade***/Perforation⁺	The development of a significant pericardial effusion during or within 30 days of undergoing an AF ablation procedure. A significant pericardial effusion is one which results in hemodynamic compromise, requires elective or urgent pericardiocentesis, or results in a 1 cm or more pericardial effusion as documented by echocardiography. Cardiac tamponade should also be classified as "early" or "late" depending on whether it is diagnosed during or following initial discharge from the hospital.
Myocardial Infarction	The presence of any one of the following criteria: 
 • Detection of ECG changes indicative of new ischemia (new ST-T changes or new LBBB) which persists for more than 1 h • Development of a new pathological Q waves on an ECG, and • Imaging evidence of new loss of viable myocardium or new regional wall motion abnormality
Stroke⁵⁸	

PRIMARY ADVERSE EVENT	DESCRIPTION / CRITERIA
Cerebrovascular Accident	
Rapid onset of a focal or global neurological deficit with at least one of the following: change in level of consciousness, hemiplegia, hemiparesis, numbness or sensory loss affecting one side of the body, dysphasia or aphasia, hemianopia, amaurosis fugax, or other neurological signs or symptoms consistent with stroke.
 
Duration of a focal or global neurological deficit ≥ 24 h; or < 24 h, if therapeutic intervention(s) were performed (e.g. thrombolytic therapy or intracranial angioplasty); OR available neuroimaging documents a new hemorrhage or infarct; or the neurological deficit results in death.
 
No other readily identifiable non-stroke cause for the clinical presentation (e.g., brain tumor, trauma, infection, hypoglycemia, peripheral lesion, pharmacological influences) †
 
Confirmation of the diagnosis by at least one of the following:
 
 • Neurology or neurosurgical specialist • Neuroimaging procedure (MR or CT scan or cerebral angiography) • Lumbar puncture (i.e., spinal fluid analysis diagnostic of intracranial hemorrhage) 
Stroke: (diagnosis as above, preferably with positive neuroimaging study)
 
 • Minor—Modified Rankin score < 2 at 30 and 90 days†† • Major—Modified Rankin score ≥ 2 at 30 and 90 days
Thromboembolism	
Formation of a clot (thrombus) inside a blood vessel causing obstruction to blood flow. The thrombus can migrate (embolus) and obstruct distal vascular sites. Diagnostic tests to help detect thromboembolisms may include but are not limited to angiography (pulmonary or distal), ventilation-perfusion (V/Q) scans, venography, Doppler ultrasonography, spiral CT, and echocardiography.

Transient Ischemic Attack⁵⁸	
New focal neurological deficit with rapid symptom resolution (usually 1 to 2 h, always within 24h. Neuroimaging without tissue injury.

Diaphragmatic Paralysis	
Absent phrenic nerve function as assessed by a sniff test. A phrenic nerve paralysis is considered to be permanent when it is documented to be present 12 months or longer following ablation.

Pneumothorax	
Introduction of air into the intrapleural cavity necessitating chest tube placement or surgical intervention.

PRIMARY ADVERSE EVENT	DESCRIPTION / CRITERIA
Heart Block	Impairment of AV conduction requiring intervention (e.g. temporary or permanent pacemaker) due to iatrogenic cause (e.g. inappropriate RF application, traumatic maneuvering of catheter or other intracardiac devices).
Pulmonary Vein Stenosis*	A reduction of the diameter of a PV or PV branch. PV stenosis can be categorized as mild <50%, moderate 50-70%, and severe 70% reduction in the diameter of the PV or PV branch. Severe PV stenosis and symptomatic PV stenosis with any degree of PV narrowing will be considered a primary adverse event and major complication of AF ablation.
Pulmonary Edema (Respiratory Insufficiency)	Respiratory insufficiency resulting in pulmonary complications necessitating intubation or other significant intervention (including diuretics administered specifically for treating pulmonary edema or ICU hospitalization requiring oxygen administration but not intubation) Exclusion criteria include: 
 • Pneumonia – infiltrate, fever and leukocytosis • Acute Respiratory Distress Syndrome
Pericarditis	Should be considered a major complication following ablation if it results in effusion which leads to hemodynamic compromise or requires pericardiocentesis, prolongs hospitalization by more than 48 h, requires hospitalization, or persists for more than 30 days following the ablation procedure.
Major Vascular Access Complication / Bleeding	
Major Bleeding: A major complication of AF ablation if it requires and/or treated with transfusion or results in a 20% or greater fall in HCT.
 
Major Vascular Access Complication: Defined as hematoma, an AV fistula, or a pseudoaneurysm which requires intervention such as surgical repair or transfusion, prolongs the hospital stay, or requires hospital admission.

* Pulmonary vein (PV) stenosis and atrio-esophageal fistula that occurs greater than one week (7 days) post-procedure shall be deemed Primary AEs.^{47,48}

** Hemodynamic compromise or instability is defined as Systolic BP < 80 mm Hg.

+ Cardiac Tamponade/Perforation occurring within 30 days of the AF ablation process will be considered Primary AEs

† Subjects with non-focal global encephalopathy will not be reported as a stroke without unequivocal evidence based upon neuroimaging studies.

†† Modified Rankin score assessments should be made by qualified individuals according to a certification process. If there is discordance between the 30 and 90 day Modified Rankin scores, a final determination of major versus minor stroke will be adjudicated by the Global Safety Monitoring Committee.

All reported Primary AEs will be monitored until they are adequately resolved or explained.

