I agree to maintain all study related information supplied by Biosense Webster, Inc. in strictest confidence. When information regarding this study is submitted to an institutional review board (IRB)/Independent Ethics Committee (IEC), it will be forwarded with a requirement that all study related material is to be held strictly confidential.

Principal Investigator
Name (PRINT)

Signature

Date

Protocol Summary

Prospective Revue of the Safety and Effectiveness of the THERMOCOOL SMARTTOUCH[®] SF Catheter Evaluated for Treating Symptomatic Persistent AF (PRECEPT)

- Title:** Prospective Revue of the Safety and Effectiveness of the THERMOCOOL SMARTTOUCH[®] SF Catheter Evaluated for Treating Symptomatic Persistent AF (PRECEPT)
- Design:** This is a prospective, multicenter, non-randomized clinical evaluation utilizing the THERMOCOOL SMARTTOUCH[®] SF catheter compared to a predetermined performance goal.
- Purpose:** The purpose of this study is to demonstrate the safety and effectiveness of the THERMOCOOL SMARTTOUCH[®] SF catheter in the treatment of drug refractory symptomatic persistent atrial fibrillation (PsAF) following standard electrophysiology mapping and RF ablation procedures.
- Enrollment:** Up to 367 subjects will be enrolled.
- Clinical Sites:** Up to 35 sites (approximately 30 in the US and up to 5 OUS).
- Subject Population:** Subjects with drug refractory symptomatic PsAF who are undergoing their first AF ablation procedure that meet the ACC/ESC/HRS criteria for persistent AF are eligible.
- Primary Endpoints:** The primary effectiveness endpoint for this study will be freedom from documented atrial fibrillation (AF), atrial tachycardia (AT), or atrial flutter (AFL) episodes through 15-month follow-up (post 3-Month Medication Adjustment Period followed by a 3-Month Therapy Consolidation period (Day 181-450)).
- The primary safety endpoint is the incidence of any early onset (within 7 days of the initial and repeat AF ablation procedure) Primary Adverse Events (AE), which are listed below:
- Death
 - Atrio-esophageal fistula*
 - Cardiac Tamponade**†/Perforation⁺
 - Myocardial infarction (MI)
 - Stroke / Cerebrovascular accident (CVA)^{†, ††}
 - Thromboembolism
 - Transient Ischemic Attack
 - Diaphragmatic paralysis
 - Pneumothorax
 - Heart block
 - PV stenosis*
 - Pulmonary edema (Respiratory Insufficiency)
 - Pericarditis
 - Major Vascular access complication / bleeding

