4.1.2 Primary Safety Endpoint

The primary safety endpoint is the incidence of any primary adverse event occurring within 7 days of the AF ablation procedure (including the initial and repeat procedures) using the study catheter per protocol.

Primary adverse events include the following conditions (refer to Table 6-1 Primary Adverse Events for detailed instructions for defining these adverse events):

- Death
- Atrio-esophageal fistula*
- Cardiac Tamponade**+/Perforation⁺
- Myocardial infarction (MI)
- Stroke / Cerebrovascular accident (CVA) †, ††
- Thromboembolism
- Transient Ischemic Attack
- Diaphragmatic paralysis
- Pneumothorax
- Heart block
- PV stenosis*
- Pulmonary edema (Respiratory Insufficiency)
- Pericarditis
- Major vascular access complication / bleeding

* Pulmonary vein (PV) stenosis and atrio-esophageal fistula that occurs greater than one week (7 days) post-procedure shall be deemed Primary AEs.^{47,48}

** Hemodynamic compromise or instability is defined as Systolic BP < 80 mm Hg.

+ Cardiac Tamponade/Perforation occurring within 30 days of the AF ablation process will be considered Primary AEs

† Subjects with non-focal global encephalopathy will not be reported as a stroke without unequivocal evidence based upon neuroimaging studies.

†† Modified Rankin score assessments should be made by qualified individuals according to a certification process. If there is discordance between the 30 and 90 day Modified Rankin scores, a final determination of major versus minor stroke will be adjudicated by the neurology members of the GSMC.

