7.2.2 Analyses for Primary Safety Endpoint

The null and alternative hypotheses are:

Hypothesis $H_0: P_S \geq 0.16$

$H_a: P_S < 0.16$

P_S : the rate of early onset (within seven days of the ablation procedure) primary AE

Null hypothesis: The rate of early onset primary AE is greater than or equal to the pre-determined performance goal of 16%.

Alternative hypothesis: The rate of early onset primary AE is less than the pre-determined performance goal of 16%.

Analysis Population: The safety population (SP) will be used as the primary analysis population. Subjects with missing primary safety data will be excluded in the primary analysis. Sensitivity analyses for missing data will be performed in the SP and are described in the Statistical Analysis Plan (SAP).

Analysis Method: The primary safety endpoint will be evaluated using the exact test for a binomial proportion at a two-sided significance level of 5%. If the upper bound of the exact two-sided 95% confidence interval of the primary safety endpoint rate is less than the performance goal of 16%, the study will be considered to have demonstrated safety.

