### 6.1.2 Primary Safety Endpoint

The primary safety endpoint is the incidence of any primary adverse event (PAE) occurring within 7 days of the AF ablation procedure (including the initial and repeat procedures) using the study catheter per protocol.

The null and alternative hypotheses are:

*Hypothesis:*  $H_0: P_S \geq 0.16$

$H_a: P_S < 0.16$

where  $P_S$  is the proportion of subjects with the early onset (within seven days of the initial and repeat ablation procedure for AF) primary AE

PAEs include the following conditions:

 
• Death
 
• Atrio-esophageal fistula*
 
• Cardiac Tamponade**/Perforation†
 
• Myocardial infarction (MI)
 
• Stroke / Cerebrovascular accident (CVA)†,††
 
• Thromboembolism
 
• Transient Ischemic Attack
 
	
 
• Diaphragmatic paralysis
 
• Pneumothorax
 
• Heart block
 
• PV stenosis*
 
• Pulmonary edema (Respiratory Insufficiency)
 
• Pericarditis
 
• Major vascular access complication / bleeding
 

---	--

- \* Pulmonary vein (PV) stenosis and atrio-esophageal fistula that occurs greater than one week (7 days) post-procedure shall be deemed Primary AEs.
- \*\* Hemodynamic compromise or instability is defined as Systolic BP < 80 mm Hg.
- + Cardiac Tamponade/Perforation occurring within 30 days of the AF ablation process will be considered Primary AEs
- † Subjects with non-focal global encephalopathy will not be reported as a stroke without unequivocal evidence based upon neuroimaging studies.
- †† Modified Rankin score assessments should be made by qualified individuals according to a certification process. If there is discordance between the 30 and 90 day Modified Rankin scores, a final determination of major versus minor stroke will be adjudicated by the neurology members of the Global Safety Monitoring Committee (GSMC).

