### **9.2 Primary Safety Endpoint**

The primary safety endpoint is the incidence of any primary adverse event occurring within 7 days of the AF ablation procedure (including the initial and repeat AF ablation procedure) using the study catheter. A performance goal of 16% is set for the primary safety endpoint. Please refer to Section 4.1 of the protocol for justifications of performance goals for the primary safety endpoint.

Based on a performance goal of 16% and an anticipated rate of 8% for the primary safety endpoint, 232 subjects will be required to obtain at least 90% power at a two-sided significance level of 0.05 using the exact binomial method.

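### Table 6-1 counts related death without a time limit under a seven-day lead-in with no exception for death, and the tested safety rate is worded as a seven-day rate although the footnotes count later events

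*Protocol*

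**What the plan says.** **Death.** Protocol 6.2.1 introduces Table 6-1 with: "A Primary AE is one of the following events occurring within seven (7) days following an AF ablation procedure with the study catheter". The first row of the table, Death, reads: "Patient death directly related to the device or procedure and occurs at any time during or after the procedure".

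**Footnoted exceptions.** Two footnotes go beyond Day 7. Pulmonary vein "stenosis and atrio-esophageal fistula that occurs greater than one week (7 days) post-procedure shall be deemed Primary AEs", and "Cardiac Tamponade/Perforation occurring within 30 days of the AF ablation process will be considered Primary AEs". They appear in the Protocol Summary, Protocol 4.1.2, Table 6-1 and SAP 6.1.2, with slightly different wording for tamponade in the Summary. None mentions death, and Death carries no footnote mark in any of the four lists.

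**Tested parameter.** Protocol 7.2.2 defines P_S as "the rate of early onset (within seven days of the ablation procedure) primary AE". In SAP 6.1.2, P_S "is the proportion of subjects with the early onset (within seven days of the initial and repeat ablation procedure for AF) primary AE". SAP 9.2 and 10.4.2 repeat the seven-day wording, and SAP 10.4.3.2 speaks of early-onset events. None of these three sections restates the exceptions.

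Protocol 4.1.2 sends the reader to Table 6-1 for the component definitions. SAP 6.1.2 lists the components by name and does not point to that table.

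**The concern.** P_S is one of only two tested parameters in a single-arm, unblinded study, so its numerator should have one definition.

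For death it does not. A device- or procedure-related death on Day 20, in a subject with no other qualifying event, is a Primary AE by the row and not one by the lead-in. The plan handles other late events with footnotes, and no footnote settles this case.

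For the window, the footnotes make certain later events Primary AEs, but P_S then counts only Primary AEs with onset within seven days. Programmed literally, it would leave out tamponade or perforation on Days 8-30 and later PV stenosis or fistula, and the reported rate would be too low. If the reading is chosen once events are known, the choice could look data-driven.

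**Working it through.** **Inputs.** Goal 16%, expected rate 8%, N=232, two-sided 0.05, exact binomial (Protocol 7.5). Success if the upper exact two-sided 95% limit is below 16% (Protocol 7.2.2). Planned 330 subjects, 367 enrolled (Protocol 7.6). Expected tamponade/perforation 2.00% (Protocol 4.1.2). The share f of tamponade starting after Day 7 is not given. I assume 5-25% and show 100% as a ceiling.

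**1. The plan's own figure.** The rule allows c events, where c is the largest count with P(X ≤ c | N, 0.16) ≤ 0.025. At N=232, c = 26 (P = 0.0247), and power is P(X ≤ 26 | 232, 0.08) = 96.8%. The stated minimum of 90% is therefore met. 232 is not the smallest such N (90% is first reached at 173), but that has no bearing here.

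**2. Distance to the pass limit.**

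| N | Last pass (upper limit) | First fail (upper limit) | Expected events at 8% | Extra events to reverse | Power at 8% |
|---|---|---|---|---|---|
| 330 | 39 (15.80%) | 40 (16.14%) | 26.4 | 40 − 26 = 14 | 99.4% |
| 367 | 44 (15.76%) | 45 (16.06%) | 29.4 | 45 − 29 = 16 | 99.7% |

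**3. One late related death.** P_S counts subjects, so a late death matters only if that subject has no other qualifying event.
- N=330: 26 events give 7.88% (upper limit 11.33%); 27 give 8.18% (11.68%).
- N=367: 29 events give 7.90% (11.15%); 30 give 8.17% (11.46%).

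Each such death moves the rate by about 0.3 points.

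**4. Seven-day reading against footnoted windows, tamponade only.** Difference in rate = 2.00% × f; in events, N × 0.02 × f.
- f = 5%: 0.1 points, 0.33 events (N=330) or 0.37 (N=367).
- f = 25%: 0.5 points, 1.65 or 1.83 events.
- f = 100%: 2 points, 6.6 or 7.3 events.

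**5. Chance of different verdicts.** Every event in the seven-day count is also in the footnoted count. The verdicts therefore differ only when the first passes and the second fails, with probability P(X ≤ m | p − 0.02f) − P(X ≤ m | p), where m = 39 or 44 and p is the rate under the footnoted windows.
- p = 8%, f = 25%: 0.9980 − 0.9941 = 0.4% (N=330); 0.9991 − 0.9970 = 0.2% (N=367).
- p = 8%, f = 100%: 0.6%; 0.3%.
- p = 10%, f = 25%: 0.9333 − 0.8818 = 5.2%; 0.9530 − 0.9099 = 4.3%.

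At p = 8% the probability cannot exceed the chance that the footnoted count fails, 1 − 0.9941 = 0.6% or 1 − 0.9970 = 0.3%. That bound holds whichever components are late.

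**6. If 8% is instead the seven-day rate.** Table 4-1 is redacted, so this cannot be excluded. Late events would then come on top.
- Adding 0.5 points (8.5%): 0.9941 − 0.9848 = 0.9% (N=330); 0.9970 − 0.9913 = 0.6% (N=367).
- Adding the full 2 points (10%): 0.9941 − 0.8818 = 11.2%; 0.9970 − 0.9099 = 8.7%. This is an extreme case.

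**The case against.** **The footnotes already settle the window.** They stand wherever the components are listed, in SAP 6.1.2 alongside P_S itself. Their only function is to override seven days; on the strict reading they would do nothing. SAP 9.2, 10.4.2 and 10.4.3.2 rely on a term defined in SAP 6.1.2, so the absence of footnotes there is ordinary drafting. This largely stands. A reader might infer that the plan intends to leave late tamponade, PV stenosis and fistula out of the tested rate, and the documents do not support that. What remains is that the parameter as worded does not match its own footnotes.

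**Row text can override the lead-in.** The tamponade row gives 30 days under the same seven-day lead-in, so related death without a time limit is the natural reading of the Death row. This is a fair argument about intent, but tamponade also has a footnote and Death does not, so the conflict is still there.

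**A third reading of death.** Because SAP 6.1.2 lists plain Death, a reader might infer that any death up to Day 7 counts, related or not. The documents do not support this. The SAP lists all 14 components by name only, and by the same logic pneumothorax or heart block would lose their criteria too. Protocol 4.1.2 refers to Table 6-1 for the definitions.

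**Materiality.** The test result is very unlikely to turn on this. That stands. The case for the change is that a primary endpoint should have one numerator and that the correction is cheap.

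**Conclusion.** The point holds as a conflict of wording in a primary endpoint. The death conflict is the firmer half: lead-in and row cannot both apply to a related death after Day 7, and no footnote decides. The P_S half is a mismatch between the tested parameter and footnotes whose intent is clear; taken literally it would understate the rate.

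The size is small. A reader might infer that the safety conclusion is in doubt, but the figures do not support that. The margin is 14 to 16 events, a late related death moves the rate by about 0.3 points, and at a true 8% under the footnoted windows the readings disagree with probability at most 0.6%. At a true 10% with a quarter of tamponade late it is 4-5%.

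These figures rest on the expected 8% and 2.00%. The late share of tamponade is my assumption. The documents as released give no late-onset rate for PV stenosis, so steps 4 and 6 do not size that component; only the bound in step 5 covers it.

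**What to change.** 1. Reconcile the death window between the Table 6-1 lead-in, the Death row and the footnotes, and carry the result into every list of components. The sponsor decides which window applies.
2. In Protocol 7.2.2 and SAP 6.1.2, define P_S as the proportion of subjects with at least one Primary AE as defined in Protocol 4.1.2 and Table 6-1, including the footnoted windows.
3. Have SAP 6.1.2 point to Table 6-1, and have SAP 9.2, 10.4.2 and 10.4.3.2 refer to that definition. This should be done before the data are analysed.

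**Cost.** The change is wording in two documents. For ablated subjects the data are already planned, since Protocol 6.1 collects adverse events throughout follow-up. The reported rate may be slightly less favourable than under a strict seven-day count. One limit should be stated: discontinued subjects (catheter inserted, no RF delivered) belong to the Safety Population but are followed for only 30 days (Protocol 3.2 and 7.1; SAP 8 and 10.2), so later events in them may not be captured.

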6.3 Serious AEs

A serious adverse event (SAE) is any event that meets one or more of the following criteria:

- Lead to a death
- Lead to a serious deterioration in the health of a subject that:
 - Resulted in a life-threatening illness or injury
 - Resulted in a permanent impairment of a body structure or a body function;
 - Required in-patient hospitalization or prolongation of existing hospitalization*
 - Resulted in medical or surgical intervention to prevent permanent impairment to body structure or a body function
- Lead to fetal distress, fetal death or a congenital abnormality or birth defect.

“Hospitalization” means the event necessitated an admission to a health care facility e.g., with at least an overnight stay. Emergency room visits that do not result in admission to the hospital should be evaluated for one of the other serious outcomes.

*Planned hospitalization for a condition present prior to the participant’s enrollment in the study will not meet the definition of an SAE but should nevertheless be included in routine study reporting.

